1.2.3. Live attenuated vaccines

In contrast to conventional inactivated and recombinant vaccines, live influenza virus vaccines are generally believed to offer broad-spectrum immune responses because they induce diverse types of adaptive responses, including serum antibodies, mucosal immunity, and induction of cytotoxic T lymphocytes, which target conserved virus epitopes (Clements 1986, Tamura 2005, Zhu 2010; Lanthier 2011, Ambrose 2012, Jin 2015). Only one such live vaccine, (FluMist[®]), which has been attenuated empirically by cold-adaptation, has been approved in the US, and is presently indicated only for persons 2-49 years of age. However, immune mechanisms conferring protection against influenza following receipt of FluMist vaccine are not fully understood; serum antibodies, mucosal antibodies, and influenza-specific T cells may play a role but there is no established surrogate of efficacy. Accumulating data also indicate that pre-existing cross-reactive immunity present in most adults limits vaccine virus replication, which in turn reduces a consistently effective immune response (Eick 2009, Ohmit 2006, Wang 2009, Monto 2009). This in part explains the observation that young, seronegative children are the population in which FluMist vaccination is typically most effective.

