2.2.2. Secondary Endpoints

The secondary endpoints are:

1. The number and percentage of study participants who after one or two doses of Bris10 M2SR or placebo demonstrate:
 - i. Influenza-specific serum antibody responses measured at specified time points;
 - ii. Influenza-specific mucosal immunoglobulin A (IgA) antibody responses measured at specified time points;
 - iii. Influenza-specific cellular immune responses measured by cytokine enzyme-linked immunospot (ELISPOT) at specified time points.
2. The number and percentage of study participants who after one or two doses of Sing2016 M2SR or placebo demonstrate:
 - i. Influenza-specific serum antibody responses measured at specified time points;
 - ii. Influenza-specific mucosal IgA antibody responses measured at specified time points;
 - iii. Influenza-specific cellular immune responses measured by ELISPOT at specified sampling time points.
3. Vaccine virus shedding evaluated by influenza A-specific qPCR on day 7 post IP administration.

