SAEs occurring at any time during the study will be recorded. Administration site and solicited AEs will be recorded through 7 days after each vaccination (Days 8 and 29) and unsolicited AEs will be recorded through 28 days after the last vaccination (Day 57). An SRC, comprised at a minimum of two independent physicians experienced in vaccine research and a biostatistician, will be available to review safety data at specified time points and as needed.

Based on the safety reviews, an intermediate or lower dose may be chosen to replace the planned dose for a dose cohort. If a lower or intermediate dose is chosen that dose will be used for an entire dose cohort. Should dosing be delayed for safety review or enrollment issues, subjects may receive their second dose at a time later than defined in the proposed dosing window.

While safety and tolerability are the primary objectives, this clinical study is also designed to assess the immune response to one and two doses of each of the investigational vaccines at each of the designated dose levels. Immunogenicity will be assessed by measuring serum antibody responses by HAI and/or microneutralization (MN) assay. Additional immune parameters will be assessed including mucosal antibody titers and cell-mediated immunity. Subjects will be pre-screened, under a site-specific Informed Consent Form (ICF), to avoid enrollment of individuals with high MN titers ($> 1:20$) against the target component (A/Singapore/INFIMH-16-0019/2016 [H3N2]).

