8.2. Secondary

Immunogenicity data sources include influenza-specific serum antibody responses (MN, HAI, ELLA) and mucosal IgA antibody responses as listed below.

External Vendor-supplied data to be integrated into the clinical database.

Vendor Name	Specimen Material Type	ISTESTCD (Test Virus)	ISSCAT (Assay Type)	Comment
Southern Research	SERUM	BRIS	MN	No LLOQ, lowest values reported = 5.
Southern Research	SERUM	SING	MN	No LLOQ, lowest values reported = 5.
Viroclinics	SERUM	BELG	MN	
Viroclinics	SERUM	BRIS	HAI	•

Viroclinics	SERUM	H6N2	ELLA	
Viroclinics	SERUM	KANS	HAI	
Viroclinics	SERUM	KANS	MN	
Viroclinics	SERUM	Hong Kong	НАІ	
Viroclinics	SERUM	Hong Kong	MN	
Viroclinics	SERUM	SING	HAI	
Viroclinics	SERUM	SWTZ	HAI	
Viroclinics	SERUM	SWTZ	MN	
		,	,	
VisMederi	NASAL MUCUS	BRIS	SIgA	LLOQ=3; set to 1.5. At the replicate level.
VisMederi	NASAL MUCUS	SING	SIgA	LLOQ=3; set to 1.5. At the replicate level.
VisMederi	NASAL MUCUS	TOTIGA	SIgA	No LLOQ.
VisMederi	NASAL MUCUS	BRISC= BRIS/TOTIGA	SIgA	BRIS to be corrected for TOTIGA. If TOTIGA <1 then BRISC= missing, otherwise BRISC=BRIS/TOTALIGA.
VisMederi	NASAL MUCUS	SINGC= SING/TOTIGA	SIgA	SING to be corrected for TOTIGA. If TOTIGA <1 then SINGC= missing, otherwise SINGC=SING/TOTIGA

Serum antibody response (influenza-specific HAI, MN, and ELLA results) after one and after both administrations of M2SR vaccine will be summarized by treatment comparisons of GMT, GMFR, seroprotection, and seroconversion (2-fold and 4-fold).

GMTs will be summarized at Days 1, 29, and 57; GMFR will be summarized by Day 29/Day 1, Day 57/Day 1, and Day 57/Day 29. Ln-transformed GMT and the Intransformed GMFR ratios will be analyzed using ANCOVA with baseline (Day 1) values as a covariate. [Note: GMFR Day 57/Day29 is modelled with Day 1 baseline covariate.]

Conversion rates categorized as >=2-fold and >= 4-fold values will be reported for Days 29 and 57. Pairwise comparisons of conversion counts (%) will be done using Fishers Exact Tests.

Seroprotection rates at Days 1, 29 and 57 will be presented for the hemagglutination inhibition (HAI) assay only. Pairwise comparisons of seroprotection counts (%) will be done using Fishers Exact Tests.

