8.4. Adjustments for Covariates

No adjustments for covariates beyond baseline values are planned.

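### HAI seroprotection at Days 29 and 57 is compared without Day 1 status, so subjects already above the threshold dilute the comparison; the size of the loss depends on a Day 1 rate the documents do not give

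*SAP*

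**What the plan says.** SAP 8.2 lists seroprotection among the summaries of serum antibody response after one and after both administrations. It says "Seroprotection rates at Days 1, 29 and 57 will be presented for the hemagglutination inhibition (HAI) assay only", followed by "Pairwise comparisons of seroprotection counts (%) will be done using Fishers Exact Tests". Neither document states the HAI titre that counts as seroprotection. Five test viruses have an HAI assay: Brisbane, Singapore, Kansas, Hong Kong and Switzerland.

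The other serum endpoints in that section do use Day 1. Conversion is a fold rise: "Conversion rates categorized as >=2-fold and >= 4-fold values will be reported for Days 29 and 57". Log titres and log fold rises "will be analyzed using ANCOVA with baseline (Day 1) values as a covariate". SAP 8.4 leaves room for this kind of adjustment and no other: "No adjustments for covariates beyond baseline values are planned".

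Protocol 2.2.2 words the endpoint as "The number and percentage of study participants who after one or two doses of Sing2016 M2SR or placebo demonstrate" an influenza-specific serum antibody response. Protocol 3.1 explains that pre-screening is meant "to avoid enrollment of individuals with high MN titers" (above 1:20) against the Singapore strain. Inclusion criterion 10 accepts a result up to 90 days old. No entry criterion concerns HAI or any other strain. SAP 1.1.2.1 says randomization was not stratified on baseline characteristics.

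**The concern.** Seroprotection is a level at a visit, whereas conversion is a change from Day 1. A subject at or above the threshold before dosing who stays there is a success at Days 29 and 57 without having responded. This happens in the placebo arm as much as in the vaccine arms. Such subjects add to both rates and carry almost no information on the vaccine.

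Day 1 positives are plausible. The entry limit is for a different assay and one strain, and four of the five HAI viruses are not that strain. Protocol 1.4.1 reports that the first-in-human study enrolled adults of the same age range with Brisbane HAI titres from below 10 up to 80. That shows such adults exist; it does not give a rate for this trial.

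The trial's stated purpose is to raise the proportion who respond serologically. If many subjects are positive on Day 1, an active dose could look little different from placebo on this endpoint.

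**Working it through.** **The plan's own figure.** The only sample-size figure is 50 per group (SAP 11), and 5 × 50 = 250 agrees with the total. No power, alpha or effect size is attached, so there is no power to reproduce. SAP 12 says enrollment stopped at about 40 per group; 40 is used below.

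**Inputs.** From the documents: n = 40 per arm and Fisher's exact test on all subjects. Assumed, because the documents are silent: two-sided 0.05; share b at or above the threshold on Day 1, from 0% to 60%; Day 1 positives stay positive; Day 1 negatives cross the threshold with probability 35% on vaccine and 3% on placebo; no dropout.

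**Dilution.** The expected rate in an arm is b + (1 − b) × r, where r is the crossing rate. The between-arm difference is therefore (1 − b) × (0.35 − 0.03). At b = 40% the rates are 0.40 + 0.60 × 0.35 = 61.0% and 0.40 + 0.60 × 0.03 = 41.8%, a difference of 19.2 points instead of 32.

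**Power.** Obtained by summing binomial probabilities over the tables that Fisher's test rejects. For the subset, each arm's number of Day 1 negatives is binomial (40, 1 − b).

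| Day 1 positive | Vaccine rate | Placebo rate | Difference (points) | Fisher, all subjects | Fisher, Day 1 negatives |
|---|---|---|---|---|---|
| 0% | 35.0% | 3.0% | 32.0 | 97% | 97% |
| 10% | 41.5% | 12.7% | 28.8 | 79% | 96% |
| 20% | 48.0% | 22.4% | 25.6 | 59% | 93% |
| 40% | 61.0% | 41.8% | 19.2 | 34% | 81% |
| 60% | 74.0% | 61.2% | 12.8 | 16% | 57% |

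Simulation of the same model agrees to within about two points (34% to 35% and 81% to 82% at b = 40%).

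**Other assumptions.**
- Crossing 40% versus 5%, b = 50%, n = 40: 29% for the planned test and 74% in Day 1 negatives. A Cochran-Mantel-Haenszel (CMH) test stratified by Day 1 status gives 81%, or 65% with continuity correction. Part of the gain over Fisher reflects Fisher's conservatism: an uncorrected chi-squared test on all subjects gives 37%.
- Same case, but 10% of Day 1 positives fall below the threshold: the stratified test drops from 81% to 59%; the subset test stays at 74%.
- Crossing 40% versus 5%, b = 30%, at the planned n = 50: 64% and 95%.
- A titre model with an assumed 1:40 cut-off and Day 1 rates of 4%, 15% and 40%: relative loss of 18% to 42%.

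**Error rate.** With no vaccine effect, the exact size of the planned test is 0.4% to 3.5% for b from 0% to 70% (n = 40 or 50), below the nominal 5%.

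**Chance imbalance.** At b = 40% the Day 1 difference between two arms has SD √(2 × 0.4 × 0.6 / 40) = 0.11, or 11 points. The unadjusted comparison carries this as noise.

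**The case against.** The strongest reply is that response is already measured elsewhere in SAP 8.2, by 2-fold and 4-fold conversion, geometric mean fold rise and baseline-adjusted analysis of log titre. In the titre model above, the planned ANCOVA has 99% to 100% power. Seroprotection is then an added display of level, with its Day 1 rate shown alongside. Both documents say the study is not powered for comparisons and that p-values are descriptive. Entry also selects for low antibody: besides the titre cap, influenza vaccination, flu-like illness and influenza treatment in the previous 6 months are excluded. High Day 1 rates are therefore undocumented, particularly for the Singapore strain. All of this stands and limits the weight of the point. It does not explain why the seroprotection comparison should ignore a Day 1 titre that is already in the data.

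A reader might also infer four stronger things that the documents do not support:
- **The comparison is biased or measures no vaccine effect.** Arms are randomized, so the difference is a genuine though diluted effect. Chance Day 1 imbalance is covered by the test's error rate, which is conservative.
- **Most of the power is lost.** In the main scenario the loss is nil at 0% Day 1 positive and 1 − 59/93 = 37% at 20%. It passes half at 40% (1 − 34/81 = 58%), and no document gives such a rate.
- **Day 1 rates are tested.** The SAP says they are presented; it does not clearly say they are compared.
- **The protocol itself rejects the label.** The remark that "serum antibodies, mucosal antibodies, and influenza-specific T cells may play a role but there is no established surrogate of efficacy" concerns the licensed live nasal vaccine, not this product.

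**Conclusion.** The point holds as a matter of precision and interpretation. The planned seroprotection comparison leaves out Day 1 status while the titre analyses beside it include Day 1. Raw rates at Days 29 and 57 mix prior titre with response, and the between-arm test is valid but less sensitive than it could be. The loss is nil with no Day 1 positives and becomes substantial from roughly 20% upward. Those figures rest on assumed crossing rates, an assumed Day 1 rate and an assumed alpha. The undefined HAI threshold is a gap whatever those values are, because both the Day 1 rate and the endpoint depend on it. As the endpoint is secondary, p-values are descriptive and other endpoints measure response directly, the severity is minor to moderate.

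**What to change.** In SAP 8.2:
1. State the HAI titre that defines seroprotection.
2. For Days 29 and 57, compare arms with Day 1 HAI taken into account. Use logistic regression with ln Day 1 HAI as covariate (Firth's method if counts are sparse) or a test stratified by Day 1 status, and name one in advance. SAP 8.4 already permits this.
3. Report the number and percentage newly at or above the threshold among subjects below it on Day 1.
4. Keep the raw rates at Days 1, 29 and 57 as a descriptive display, and state that Day 1 is not tested.

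The titres are already collected. The cost is SAP wording and one extra table for each of the five HAI viruses. The denominator for new crossings shrinks where Day 1 titres are high: at 40% Day 1 positive, 40 × 0.6 = 24 per arm are expected. It would also help to say which pairs are compared, since all pairs would mean 10 pairs × 5 viruses × 2 visits = 100 comparisons.

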8.2.1. Secretory IgA Immune Response and Viral Shedding from Nasal Swab

Summary statistics for secretory IgA immune response (influenza A-specific and total IgA ELISA) at Days 1 (baseline), 29, and 57 post IP administration will be provided.

Summary statistics for viral shedding (influenza A-specific q-PCR) at Screening, Days 1 and 8, will be provided.

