2.1.2. Secondary Objectives

The secondary objectives are:

1. To assess the immunogenicity (serum antibody, mucosal antibody and cellular immune responses) of one and two administrations of Bris10 M2SR vaccine at 10^8 TCID₅₀.
2. To assess the immunogenicity (serum antibody, mucosal antibody and cellular immune responses) of one and two administrations of Sing2016 M2SR vaccine at 10^8 , $10^{8.5}$ and 10^9 TCID₅₀.
3. To evaluate vaccine virus shedding after intranasal delivery.

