8. STATISTICAL METHODS AND CONSIDERATIONS

8.1. General Considerations

Prior to the analysis of the study data, statistical methods and table shells will be detailed in a Statistical Analysis Plan (SAP) and finalized before database lock.

The final analysis will be done after the last subject has had the day 57 visit and the data base has been locked. The day 209 data will be included as a supplemental analysis.

Statistical analysis will be the responsibility of Northrim Consulting, Inc, using SAS® (SAS Institute Inc., Cary, NC, USA; version 9.4 or higher).

There are primary, secondary and exploratory objectives, endpoints and analyses. Depending upon the result of the primary and secondary analyses, not all exploratory analyses may be done.

Safety and subject disposition analyses will be conducted on the safety analysis set.

Summarization of primary and secondary efficacy endpoints will be done using FAS. These summaries may be repeated using the PP analysis set.

There are no formal tests of hypotheses in this study. Efficacy outcomes are descriptive only.

The data will be summarized in tables listing the number, mean, standard deviation, median, minimum, maximum, standard error (SE) and a 95% CI of subjects for continuous data, or in tables listing count and percentage for categorical data where appropriate. Tables will be presented by IP treatment and overall. Data listing by subject will be provided.

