8.3.4. Additional Analyses

Additional analyses will be descriptive only; p-values are descriptive and not corrected for multiple testing.

Immunogenicity

Serum antibody, mucosal antibody and cellular immune response will be summarized using descriptive statistics by sampling timepoint for all subjects and by baseline values.

Seroconversion rates will be presented by timepoint and by baseline starting values.

Viral shedding will be summarized using descriptive statistics.

Additional (exploratory) endpoints may be analyzed.

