5. DEMOGRAPHIC AND BASELINE CHARACTERISTICS (SS)

N (%) of subject will be displayed by treatment for gender, race, age, ethnicity, height, weight, BMI, and Investigational Site. Summary statistics (N, Mean, SD, Median, Min, Max) will be displayed for continuous variables. N(%) will be displayed for categorical variables.

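### SAP 8.2.1 gives mucosal IgA only unspecified summary statistics of the level, while serum assays in the same objective get ln-scale, baseline-adjusted comparisons

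*SAP*

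**What the plan says.** Protocol 2.1.2 places mucosal antibody beside serum antibody, after one dose and after two: "To assess the immunogenicity (serum antibody, mucosal antibody and cellular immune responses) of one and two administrations of Sing2016 M2SR vaccine". The matching objective for Bris10 has the same form, and Protocol 2.2.2 lists mucosal IgA as a secondary endpoint for both vaccines.

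For serum, SAP 8.2 is specific: "Serum antibody response (influenza-specific HAI, MN, and ELLA results) after one and after both administrations of M2SR vaccine will be summarized by treatment comparisons" of geometric mean titre, geometric mean fold rise (Day 29/1, 57/1 and 57/29), seroprotection and conversion. The ln-transformed titres and fold rises "will be analyzed using ANCOVA with baseline (Day 1) values as a covariate".

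For mucosal IgA, SAP 8.2.1 has one sentence: "Summary statistics for secretory IgA immune response (influenza A-specific and total IgA ELISA) at Days 1 (baseline), 29, and 57 post IP administration". The SAP 8.2 data table defines four virus-specific IgA variables: SING and BRIS (values below the limit of 3 set to 1.5), and SINGC and BRISC (each divided by total IgA, and missing if total IgA is below 1).

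SAP 8.2.1 does not say what its summary statistics are. Elsewhere the SAP spells the term out. In section 5 it reads "Summary statistics (N, Mean, SD, Median, Min, Max) will be displayed for continuous variables", and section 9.2.1 gives the same list, without N, for oral temperature. The protocol's general rule is similar: "The data will be summarized in tables listing the number, mean, standard deviation, median, minimum, maximum, standard error (SE) and a 95% CI".

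Protocol 8.3.4 adds: "Serum antibody, mucosal antibody and cellular immune response will be summarized using descriptive statistics by sampling timepoint for all subjects and by baseline values". The SAP does not carry the split by baseline values over to IgA, and SAP 8.8 plans no subgroup analyses.

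**The concern.** A response to an intranasal vaccine, and any further rise from the second dose, are changes within a subject. A table of levels at three visits shows neither the rise from Day 1 nor the step from Day 29 to Day 57. It also leaves the variation in pre-existing nasal IgA in every between-arm comparison, although each subject has a Day 1 swab scheduled (Protocol Table 3).

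The scale matters too. These variables are bounded below and are concentrations or ratios, so right skew is plausible, although the documents give no distribution. If the tables show arithmetic means, a few high swabs can dominate them.

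At stake is whether the mucosal result can be read beside the serum result, and against the one-dose and two-dose objective, with only about 40 subjects per arm (SAP 12). SAP 12 also says ELISPOT and shedding data were unavailable at lock. IgA is therefore the only non-serum immune endpoint among the secondary endpoints in this analysis.

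**Working it through.** **No plan figure to reproduce.** The 50 per group is empirical and the study is declared unpowered (SAP 11). The plan gives no SD, correlation or target effect for IgA.

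**Inputs.** From the documents: n = 40 per arm (SAP 12). Assumed: ln-scale SD σ of 0.5 to 1.3, correlation ρ between the ln Day 1 and ln follow-up values of 0.3 to 0.7, true geometric mean ratio versus placebo of 1.5 or 2.0, and lognormal IgA.

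**Step 1: variance of a between-arm difference on the ln scale.**
- Unadjusted level: 2σ²/n
- ANCOVA on ln Day 1: (2σ²/n)(1 − ρ²)
- Fold rise: (2σ²/n) × 2(1 − ρ)

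| ρ | ANCOVA, 1 − ρ² | Variance saved | 40 per arm is worth | Fold rise, 2(1 − ρ) |
|---|---|---|---|---|
| 0.3 | 0.91 | 9% | 40/0.91 = 44 | 1.40 |
| 0.5 | 0.75 | 25% | 40/0.75 = 53 | 1.00 |
| 0.7 | 0.51 | 49% | 40/0.51 = 78 | 0.60 |

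Fold rise alone is therefore less precise than the plain level below ρ = 0.5, equal at 0.5 and better only above it.

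**Step 2: CI width.** With σ = 1.0, the 95% limits for a ratio are the estimate multiplied and divided by exp(1.99 × √(2/40) × √(1 − ρ²)). Unadjusted, this is exp(1.99 × 0.2236) = 1.56. With ANCOVA it is 1.53, 1.47 and 1.37 at ρ = 0.3, 0.5 and 0.7.

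**Step 3: separating scale from baseline adjustment.** The simulation used 40 per arm and 20,000 replicates per row, with ρ = 0.5. It compared a Welch test on raw follow-up levels, a t-test on ln levels, and ANCOVA on the ln scale. Entries are the chance that a two-sided 95% CI excludes no difference.

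| True ratio | ln-SD | Raw means | Unadjusted ln level | ln ANCOVA |
|---|---|---|---|---|
| 2.0 | 0.5 | 100% | 100% | 100% |
| 2.0 | 0.8 | 90% | 97% | 99% |
| 2.0 | 1.0 | 68% | 86% | 94% |
| 2.0 | 1.3 | 38% | 65% | 78% |
| 1.5 | 0.5 | 92% | 95% | 98% |
| 1.5 | 0.8 | 49% | 61% | 73% |
| 1.5 | 1.0 | 30% | 43% | 54% |
| 1.5 | 1.3 | 15% | 28% | 35% |

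At ratio 2.0 and ln-SD 1.0, the total gain is 94 − 68 = 26 points. Of these, 86 − 68 = 18 come from the log scale and 94 − 86 = 8 from the Day 1 covariate.

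**Step 4: the covariate alone at other correlations.** Over ln-SD 0.8 to 1.3 and both ratios, it adds about 1 to 4 points at ρ = 0.3 and up to about 27 at ρ = 0.7.

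**Limit.** The simulation ignores the floor at 1.5 and missing ratios, both of which would alter these figures.

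**The case against.** The strongest reply is that the arithmetic scale is inferred. SAP 8.2.1 sits inside 8.2, where the convention for immunogenicity is geometric. The definitions of the term come from demographics and temperature, and Protocol 8.1 names no scale. A statistician who reported geometric means would breach nothing and would recover most of the gain in Step 3. The listed median is also not driven by a few high swabs. This stands: the plan leaves the scale open and does not exclude logs. Arithmetic remains the likelier reading, because the SAP states ln where it wants ln.

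A reader might also infer that Day 1 is not used at all. That goes too far. Day 1 is tabulated, Protocol 8.3.4 plans summaries by baseline values, and SAP 8.4 contemplates baseline adjustment without limiting it to serum. What is missing is a stated paired or adjusted analysis of IgA.

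Finally, the study is descriptive, unpowered and primarily about safety, and Protocol 8.3.4 promised only descriptive statistics for mucosal antibody. That limits the consequence, and the subject-level values remain available for later analysis. It does not explain the difference in treatment, since the serum results are equally descriptive and still receive ANCOVA. An interval that describes an effect is more useful when it is narrower and on a readable scale.

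**Conclusion.** The point holds as a gap in specification with an inexpensive remedy. SAP 8.2.1 names no scale, no within-subject change and no baseline-adjusted comparison for a secondary endpoint whose serum counterpart has all three.

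A reader might conclude that the endpoint loses much of its precision. The documents do not support that as a flat statement, because it depends on an SD and a correlation they do not give. On the ln scale, the saving from Day 1 ranges from slight (9% of variance at ρ = 0.3) to substantial (49% at ρ = 0.7). The larger contrast of 68% against 94% also requires that the tables use raw means of skewed data. At ln-SD 0.5 and ratio 2.0 all three methods exclude no difference essentially always, although the adjusted interval is still narrower.

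Nor should fold rise be read as a cure for imprecision, since it gains only above ρ = 0.5. Its value is that it shows the response to one dose and to two.

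The lack of an IgA responder definition for the number-and-percentage endpoint in Protocol 2.2.2 is a separate matter.

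**What to change.** In SAP 8.2.1, extend the serum analysis to SING, BRIS, SINGC and BRISC:
- Report geometric means at Days 1, 29 and 57.
- Fit ln-scale ANCOVA at Days 29 and 57 with the ln Day 1 value as covariate, and report treatment ratios with descriptive 95% CIs.
- Add geometric mean fold rises for Day 29/1, 57/1 and 57/29, to show the one-dose and two-dose responses.
- Keep the arithmetic summary and the median as supportive.

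The cost is a short SAP change and reuse of the serum ANCOVA programs, with no new data, visits or subjects. It adds a few more descriptive comparisons, uncorrected as SAP 8.7 already allows. Subjects without a usable Day 1 value, including those whose Day 1 total IgA is below 1 for the corrected variables, drop out of the adjusted and fold-rise results because SAP 8.5 imputes nothing. The number analysed should therefore be shown beside each estimate.
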